7.8 Definition of a Serious Adverse Event

A **serious adverse event (SAE)** is any adverse event occurring within the timelines specified in the protocol that results in any of the following outcomes:

- Death
- Life-threatening situation (subject is at immediate risk of death)
- Inpatient hospitalization or prolongation of existing hospitalization
- Persistent or significant disability/incapacity
- Congenital anomaly/birth defect in the offspring of a subject who received study drug
- Important medical events that may not result in death, be immediately life-threatening, or require hospitalization, may be considered an SAE when, based upon appropriate medical judgment, they may jeopardize the subject and may require medical or surgical intervention to prevent one of the outcomes listed in this definition. Examples of such events are intensive treatment in an emergency room or at home for allergic bronchospasm; blood dyscrasias, or convulsions that do not result in hospitalization; or development of drug dependency or drug abuse

7.9 Clarification of Serious Adverse Events

The following are clarifications of the above definitions of SAEs:

- “Inpatient hospitalization” does not require inclusion of elective surgery; however, any adverse event occurring during that hospitalization that prolongs the hospital stay would be an SAE
- “Inpatient hospitalization” does not have a requirement to be greater than a twenty-four hour stay. If the subject was admitted to the hospital for less than a day for the purpose of treatment or observation, the definition of “Inpatient hospitalization” is met. Brief treatment in an outpatient clinic or Emergency department does not constitute “inpatient hospitalization.”
- Complications that occur during hospitalizations are AEs. If a complication prolongs hospitalization, it is an SAE

- “Life-threatening” means that the subject was at immediate risk of death from the event as it occurred. This does not include an event that might have led to death, if it had occurred with greater severity
- The Investigator should attempt to establish a diagnosis of the event based on signs, symptoms, and/or other clinical information. In such cases, the diagnosis should be documented as the AE/SAE and not the individual signs/symptoms

7.10 Prompt Reporting of SAEs to Sponsor

The Sponsor has requirements for reporting serious adverse events to regulatory agencies for a drug under clinical investigation. The Sponsor must be notified within **24 hours of discovery** and the Investigator determines that an adverse event meets the protocol definition of an SAE. All SAEs occurring from the beginning of study IUS insertion through 30 days after IUS discontinuation (through the 30-Day Safety Follow-up Visit for expulsions of unknown date) require reporting to the Sponsor. Investigators should not wait to receive additional information to fully document the event prior to notifying the Sponsor but should provide as much relevant information as immediately available. Further details of the event can be provided as they become available. The procedures for reporting SAEs are as follows:

- Complete the “Serious Adverse Event Report” form
- Fax the Serious Adverse Event form to Sponsor
- For fatal or life-threatening events, also fax copies of hospital case reports, autopsy reports, and other documents when requested and applicable
- The Sponsor may request additional information from the Investigator to ensure the timely completion of accurate safety reports
- Any fatal or life-threatening events should also be reported immediately by telephone to the Sponsor
- The SAE form should be completed as thoroughly as possible and signed by the Investigator before transmittal to Sponsor. However, submission of SAEs should not be delayed waiting for an Investigator signature. It is also very important that the Investigator provides an assessment of the causal relationship between the event and the study drug at the time of the initial report (see 7.12.2 for Causality definitions)

- The Investigator, or responsible person according to local requirements, must comply with the applicable local regulatory requirements concerning the reporting of SAEs to regulatory authorities and the IRB

7.11 Clinical Laboratory Abnormalities and Other Abnormal Assessments as Adverse Events and Serious Adverse Events

Abnormal laboratory findings (e.g., clinical chemistry, hematology) or other abnormal assessments (e.g., electrocardiogram, X-rays, vital signs) *per se* are not reported as AEs. However, abnormal findings that are deemed **clinically significant** (i.e., associated with signs and/or symptoms or requiring therapeutic intervention) must be recorded as AEs if they meet the definition of an adverse event (and recorded as an SAE if they meet the criteria of being serious) as described previously. Clinically significant abnormal laboratory or other abnormal findings that are detected after IUS insertion or that are present at baseline and worsen following study IUS insertion are included as AEs (and SAEs if serious).

The Investigator should exercise his or her medical judgment in deciding whether an abnormal laboratory finding or other abnormal assessment is clinically significant. A clinically significant laboratory abnormality in the absence of clinical symptoms may also jeopardize the subject and may require intervention to prevent immediate consequences (e.g., a markedly high serum potassium concentration may not be accompanied by arrhythmia, yet be of a magnitude to require potassium-binding resin administration to prevent such sequelae). Subjects should undergo repeat testing of clinically significant abnormal laboratory findings as soon as they are recognized.

7.12 Reporting of Adverse Events

Any AE occurring from the beginning of the IUS insertion procedure until 30 days after IUS discontinuation must be documented in the subject's study records and appropriate CRF.

7.12.1 Adverse Event CRFs

Specific Adverse Events are recorded on different CRFs.

AEs related to bleeding or cramping/pain

- With insertion - report on the IUS Insertion Questionnaire CRF
- With removal - report on the IUS Removal Questionnaire CRF
- During IUS use
 - Months 1-24:
 - The subject's diary acts as the menstrual bleeding or cramping/pain AE CRF
 - Menstrual bleeding or cramping/pain should also be reported on the general AE CRF only if:
 - Bleeding or cramping/pain are not related to the IUS or a menstrual condition
 - Bleeding or cramping/pain meet serious criteria; an SAE report would also have to be submitted (this exception is due to data system requirements)
 - Bleeding or cramping/pain result in the IUS being removed (this exception is due to data system requirements)
 - Months 25-121
 - Starting at Month 27 (phone contact), study sites will begin to assess menstrual bleeding/cramping for the prior 3 months (from Month 25; the subject will be asked to characterize her bleeding/cramping pattern for the prior 3 months and compare to when she was not using hormonal contraception prior to study entry)
 - Menstrual bleeding or cramping/pain should also be reported on the general AE CRF if:
 - Bleeding or cramping/pain is indicated as worse in severity or frequency than when the subject was not using hormones on the Bleeding/Cramping Form (verify against Menstrual History)
 - Self-reported by the subject for any months not included in the form (e.g., subject missed last contact so no form was completed) and worse in severity or frequency than when the subject was not using hormones (verify against Menstrual History)

- Bleeding or cramping/pain meets serious criteria (see section 7.8)

7.12.2 Causality Assessment: Adverse Event Relationship

The Investigator's causality assessment should consider the potential etiologies for the observed adverse event. An adverse event may be related to the study drug, other concomitant medications, the underlying disease pathology, intercurrent illness, a procedure performed in the course of the study, or another reason. Among the potential etiologies, the Investigator should make a determination based on the most likely causal relationship. When a causality assessment is provided for a serious adverse event, it is important to include a rationale for the assessment so that a better understanding of the reported event can be compiled. The rationale should be accompanied by all available supporting evidence, including relevant laboratory tests, histopathology evaluations and the results of other diagnostic procedures. The Investigator's rationale with supporting evidence is valuable when the Sponsor performs a cumulative analysis of similar events.

The Investigator will assess the relationship of the AE to the study IUS or the IUS insertion or removal procedures by using the following general guidelines:

Not Related: A causal relationship between the study IUS/procedures and the AE can be ruled out (e.g., based on the temporal sequence, absence of a reasonable pathophysiological mechanism, or direct evidence of actual cause).

Unlikely related: A clinical event, including a laboratory test abnormality, with a temporal relationship to IUS insertion or the onset of an IUS insertion or removal procedure which makes a causal relationship improbable, and in which other drugs, chemicals or underlying disease provide plausible explanations.

Probably Related: A clinical event, including a laboratory test abnormality, with a reasonable time sequence to IUS insertion or the onset of an IUS insertion or removal procedure, unlikely to be explained by concurrent disease or other drugs or chemicals. Information on drug withdrawal may be lacking or unclear.

Related: A clinical event, including a laboratory test abnormality, with a reasonable time sequence to IUS insertion or the onset of an IUS insertion or removal procedure, cannot be

attributed to concurrent disease or other drugs or chemicals, and which follows a clinically reasonable response on withdrawal.

7.12.3 Adverse Event Severity

The Investigator will assess the severity of the AE using the following general guidelines:

- **Mild:** An AE that is usually transient, requiring no special treatment, and does not interfere with the subject's daily activities
- **Moderate:** An AE that introduces a low level of inconvenience or concern to the subject and may interfere with daily activities, but is usually ameliorated by simple therapeutic measures
- **Severe:** An AE that interrupts a subject's usually daily activity and typically requires systemic drug therapy or other treatment (a severe AE may not necessarily qualify as a SAE)
- **Life-threatening:** An AE that put the subject at immediate risk of death from the event as it occurred. This does not include an event that might have led to death if it had occurred with greater severity

7.12.4 Adverse Event Outcome

The Investigator will categorize the outcome of each Adverse Event according to the definitions below:

- **Resolved:** The subject recovered from the AE
- **Resolved with sequelae:** A condition whereby the consequences of a disease or injury include lingering effects
- **Ongoing:** At the time of the last assessment, the event is ongoing, with an undetermined outcome. Note: Ongoing AEs are not considered resolved as a result of death and no AE stop date should be recorded for an AE that is ongoing at the time of death

- **Fatal:** Adverse Event directly caused death. The Sponsor may request that the Investigator perform or arrange for the conduct of supplemental measurements and/or evaluations. If a subject dies during participation in the study or during a recognized follow-up period, the Sponsor should be provided with a copy of any post-mortem findings, including histopathology
- **Unknown:** The outcome is not known and cannot otherwise be categorized

The Investigator should attempt to establish a diagnosis of the event based on the signs, symptoms and/or other clinical information. In such cases, the diagnosis should be documented as the AE (and SAE if serious) and not the individual signs/symptoms.

In the case of abnormal labs or diagnostic tests judged to be clinically significant by the Investigator a diagnosis, if known, or clinical signs or symptoms if the diagnosis is unknown, rather than the clinically significant laboratory finding or abnormal assessment, should be used to complete the AE/SAE page. If no diagnosis is known and clinical signs or symptoms are not present, then the abnormal finding should be recorded on the AE/SAE page. If an SAE report is completed, pertinent laboratory data should be recorded on the SAE form, preferably with baseline values and copies of laboratory reports.

7.13 Clarification of Action Taken with IUS

The Investigator will categorize the Action Taken with IUS according to the definitions below:

- **None:** The IUS was not removed as result of the Adverse Event
 - the IUS was left in place
 - the IUS was removed at the time of the AE but due to a different AE or reason
 - the IUS was already removed prior to the AE start date
 - the AE was a full expulsion
 - the subject was LTFU
- **IUS Removed for Non-Safety Reasons:** The IUS was removed for an Adverse Event even though the IUS could have remained in place without placing the subject at risk for a serious complication

- **IUS Removed for Safety Reasons:** The IUS was removed for an Adverse Event because the subject was at risk for a serious complication as a direct result of the AE if the IUS had not been removed
- **Unknown:** The IUS was removed by another provider

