7.1.7 Menstrual Changes

Women who use a LNG IUS experience a change in menstrual bleeding patterns. Most commonly, women experience irregular bleeding and spotting in the first 3-6 months after

insertion. The average number of days of bleeding and spotting decline over the first year with an average of less than 2 days of bleeding per month by the end of one year (Andersson 1994). Approximately 20% of women are amenorrheic for a period of 90 days or more by the end of the first year of use (Andersson 1994). In a U.S. study, approximately 80% of Mirena users rated their bleeding as much lighter at the end of 12 months of use compared to 4% of subjects who considered their bleeding to be heavier (Jensen). Approximately 70% of women rated the changes in their bleeding as beneficial.

Hemoglobin values increase with LNG IUS use by an average of 2.4 g/dL at 3 months and 1.8 g/dL at 12 months (Luukkainen). The hemoglobin levels then appear to remain stable with a mean increase of 1.6 g/dL at 5 years (Andersson 1994). The increases are related to starting levels as women with a lower hemoglobin initially experience a greater increase (Luukkainen).

Discontinuation because of bleeding problems is reported to occur in approximately 7.3 per 100 women in the first year and 15 per 100 women cumulatively over 5 years (Andersson 1994).

Approximately 4 per 100 women discontinue because of amenorrhea. Such removals may be avoided with better counseling. In a recent US trial, 3.5% of women discontinued Mirena in the first year because of complaints related to bleeding (Jensen). This lower rate may be related to better counseling regarding the expected bleeding or a difference in the subject population.

Possible bleeding changes with the LNG20 in this study are not expected to pose a substantial risk to the subject's health but rather an inconvenience.

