9.8 Key Secondary Outcomes

The Pearl Index analysis described above for the primary outcome will also be performed for use during years 3, 4, 5, 6, 7, 8, 9 and 10 using the MITT population. The Pearl Index will be calculated for use during years 3, 4, 5, 6, 7, 8, 9 and 10 with a goal of each having acceptable precision (defined as the upper bound of the 95% confidence interval being no more than 1 unit above the point estimate). Other Secondary Outcomes

All secondary outcomes will be analyzed using the Safety Population unless noted otherwise.

- **Pregnancy Rates**

Pearl indices and life table pregnancy analyses will also be prepared for the PP population during years 3, 4, 5, 6, 7, 8, 9 and 10 unless the populations are essentially the same as the MITT population. Kaplan-Meier methods will be used to estimate the cumulative pregnancy percentage for years 1 through 10 for each treatment group using the MITT population.

- **IUS Continuation Rates**

Cumulative IUS continuation rates at 1 year, 2 years, 3 years, 4 years, 5 years, 6 years, 7 years, 8 years, 9 years and 10 years will be summarized for each treatment group, as applicable, using Kaplan-Meier methods.

- **IUS Expulsion Rates**

Cumulative IUS expulsion rates at 1 year, 2 years, 3 years, 4 years, 5 years, 6 years, 7 years, 8 years, 9 years and 10 years will be summarized for each treatment group, as applicable, using Kaplan-Meier methods.

- **IUS Safety-Related Removal Rates**

Cumulative IUS safety-related removal rates at 1 year, 2 years, 3 years, 4 years, 5 years, 6 years, 7 years, 8 years, 9 years and 10 years summarized for each treatment group, as applicable, using Kaplan Meier methods.

- **Vaginal Bleeding Patterns**

Vaginal bleeding patterns (none, spotting, and light, normal, or heavy flow [bleeding]) will be summarized by incidence and duration of bleeding. Baseline vaginal bleeding is recorded on the Menstrual History CRF based on menstrual characteristics when not using hormonal contraception.

Based on WHO terminology, bleeding and spotting are defined as:

- Bleeding: any bloody vaginal discharge for which protection, such as pads is used.
- Spotting: any bloody vaginal discharge for which protection is not used (for women who use mini pads for daily protection, extra protection is not required); if spotting and bleeding occur on the same day, it is recorded as a bleeding day.

- **Dysmenorrhea**

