The site should check for the IUS strings by palpation or direct visualization at each study visit. Ultrasound examination to verify the IUS is in place cannot substitute for checking the strings. If the strings are not evident on exam follow these steps, moving to the next one if unsuccessful:

- Use endobrush in cervical canal to attempt to tease down string.
- Perform a transvaginal ultrasound examination to locate the IUS. If the IUS is confirmed to be present in the uterus and the strings are missing, then transvaginal ultrasonography should be performed at all annual follow-up visits to confirm presence of the IUS.
- Obtain a flat plate abdominal x-ray to check if the IUS is within the abdomen.
 - If it is not visible on abdominal x-ray, the case will be considered a spontaneous expulsion.
 - If it is visible on x-ray, but not within the uterus on ultrasound, the case will be considered a perforation. The patient should then be referred, as necessary, for IUS removal by laparoscopy or laparotomy, and for any other necessary care.
- If the IUS has been expelled or must be removed, the subject cannot receive another IUS and must be discontinued from the study.

4. Partial Expulsion

Defined as visual evidence of the lower portion of the IUS stem protruding through the cervical os OR evidence of increased bleeding and/or cramping complaints with the presence of the IUS in the lower uterine segment. The system can be expelled from the uterine cavity without the woman noticing it, resulting in the loss of contraceptive protection. As menstrual flow typically decreases after the first 3 to 6 months of IUS use, an increase of menstrual flow may be indicative of an expulsion.

- The IUS should be removed and the subject discontinued from the study.
- The subject cannot receive another IUS through the study.

5. Infection

- Patients must be taught to recognize and report to their physician promptly any symptoms of pelvic inflammatory disease. These symptoms include development of menstrual disorders (prolonged or heavy bleeding), unusual vaginal discharge, abdominal or pelvic pain or tenderness, dyspareunia, chills, and fever. Following a diagnosis of PID, or suspected PID, bacteriologic specimens should be obtained and antibiotic therapy should be initiated promptly.

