11.9 Continuation, Expulsion, and Removal Rates

Cumulative rates of IUS continuation, expulsion, and safety-related removal at 6 months, Years 1, 2, 3, 4, 5, 6, 7, 8, 9 and 10 will be summarized. Time to event will be calculated as the date of continuation/expulsion/removal minus the date of IUS insertion plus one. Subjects without a continuation/expulsion/removal will be censored at the last contact date (as described in Section 5.4) and failure time will be calculated as the last contact date minus the date of IUS insertion plus one. Subjects who report an expulsion that is not confirmed by the study site will be censored. The safety-related removal rates may also be summarized by MedDRA preferred term in the same manner.

Expulsion rates including analysis of complete and partial expulsions by inserter type, parity and duration of use (by year) in the Safety Population will also be summarized.

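### The 'Unknown' action-taken code is defined by who removed the IUS rather than why, and neither document says which codes count as a safety-related removal

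*Protocol*

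**What the plan says.** Protocol 7.13 gives the investigator a list of actions taken with the IUS after an adverse event. Two removal codes rest on the reason:

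- 'Safety Reasons' applies when the device came out "because the subject was at risk for a serious complication as a direct result of the AE if the IUS had not been removed".
- 'Non-Safety Reasons' applies when "The IUS was removed for an Adverse Event even though the IUS could have remained in place without placing the subject at risk" of a serious complication.

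The third, 'Unknown', has one criterion: "The IUS was removed by another provider". It does not require that the reason be missing.

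The endpoint appears in both documents. Protocol 9.8 plans "Cumulative IUS safety-related removal rates at 1 year" and at each later year to year 10, by Kaplan-Meier. SAP 11.9 plans "Cumulative rates of IUS continuation, expulsion, and safety-related removal at 6 months" and then yearly to year 10, with women who have no event censored at last contact. Neither section refers to the 7.13 codes or mentions 'Unknown'.

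Removals away from the study site are expected. Protocol 6.6 allows for a device already removed at an outside location. For a device seen on x-ray but not in the uterus, Appendix C (item 3, Missing Strings) says: "The patient should then be referred, as necessary, for IUS removal by laparoscopy or laparotomy".

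**The concern.** Protocol 7.13 is the only place that separates safety from non-safety removals, so the endpoint has to draw on it in some way. A code defined by the provider does not fit a scale otherwise defined by reason. A site that follows the definition literally can record 'Unknown' for a removal whose safety reason is fully documented. If the programmer then counts only 'Safety Reasons', that woman becomes a non-event.

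The error has one direction. No step moves a non-safety removal into the event count, but safety removals can leave it. Some of those could be serious, for example a perforated device removed surgically after referral. At stake is the accuracy of a listed secondary safety outcome reported to 10 years.

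**Working it through.** The documents give no expected rate or precision for this endpoint, so there is no figure to reproduce. The check is a comparison of text, followed by arithmetic to show scale.

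**Text comparison**

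1. Take a removal by another provider for an adverse event that put the woman at risk of a serious complication. It meets 'Unknown' (another provider) and 'Safety Reasons' (which is not limited to site removals). Protocol 7.13 gives no precedence.
2. Protocol 7.12.4, immediately before, also has an 'Unknown' category, for adverse-event outcome. That one is reserved for outcomes that are not known and fit no other category. The 7.13 code lacks this condition.
3. Protocol 9.8 and SAP 11.9 name the endpoint without mapping it to the codes, so the treatment of 'Unknown' is left to whoever programs the table.

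**Scale: any safety removal**

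Let u be the share of true safety removals coded 'Unknown' and not counted. The crude counted rate is (1 − u) times the true rate: 0.90, 0.75 and 0.50 of the truth for u = 10%, 25% and 50%. The documents do not give u; these values are assumptions.

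**Scale: perforation**

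Inputs: 1,600 LNG20 women aged 16-35 plus about 150 aged 36-45 (Protocol synopsis, Sample Size), and about 1 perforation per 1,000 insertions (Protocol 7.1.5).

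- Women: 1,600 + 150 = 1,750.
- Expected perforations: 1,750 × 1/1,000 = 1.75.
- Chance of at least one: 1 − 0.999^1,750 = 0.83.
- Absolute loss if all were coded 'Unknown': 1.75 / 1,750 = 0.1 per 100 women, as a crude proportion.

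The relative loss depends on the rate S of other safety removals, which is assumed. With q the share of perforations coded 'Unknown', the loss is 0.1q / (S + 0.1):

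| S (per 100) | q = 1 | q = 0.25 |
|---|---|---|
| 0.5 | 0.1/0.6 = 17% | 0.025/0.6 = 4% |
| 1 | 0.1/1.1 = 9% | 0.025/1.1 = 2% |
| 2 | 0.1/2.1 = 5% | 0.025/2.1 = 1% |

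These are crude proportions. In a Kaplan-Meier estimate a removal late in follow-up weighs more, because fewer women remain at risk.

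**The case against.** The strongest reply is that nothing in the documents says an outside removal is lost. The codes overlap, so a site may properly choose 'Safety Reasons' when it knows why the device came out, and the SAP may intend that. This stands against any claim that all outside removals disappear. It does not remove the ambiguity, because the literal definition points to 'Unknown' and no rule overrides it.

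A reader might also infer that the protocol sends perforations to outside surgeons as its standard route, so that the gravest removals are the ones lost. The text does not go that far. Referral is conditional and sits in the missing-strings steps. Appendix C item 2 describes a transcervical attempt for a device partly in the uterine wall, and laparoscopy by an experienced clinician who is not said to be outside the study. Perforation is also reported separately (Protocol 9.8, SAP 11.8).

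A further tempting inference is that the endpoint misses most removals for harm because 'Non-Safety' removals are left out. Protocol 7.1.7 says: "Discontinuation because of bleeding problems is reported to occur in approximately 7.3 per 100 women in the first year". Its 5-year figure is 15 per 100, and Protocol 7.1.6 gives 4.2 per 100 for pain, so 15 + 4.2 = 19.2. Set against under 1 per 100 removed for pelvic inflammatory disease (Protocol 7.1.4), the share counted would be at most about 1 / 20.2 = 5%. That figure assumes that every bleeding and pain removal is coded 'Non-Safety' and that pelvic inflammatory disease is the only safety reason. The choice of background rate also matters. In year 1 the sum is 7.3 + 1.6 = 8.9 per 100 from one cited trial, but 3.5 + 2.4 = 5.9 from the cited US trial. More fundamentally, the exclusion is the endpoint's stated definition. Those events are still recorded (Protocol 7.7), tabulated by reason for discontinuation (SAP 7.1) and reflected in the continuation rate (SAP 11.9). SAP 11.2 does list no table of adverse events leading to removal, but that is a reporting preference.

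Finally, the outcome is descriptive and SAP 5.1 plans no formal tests. That limits the consequence but does not justify leaving the event undefined.

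**Conclusion.** The point holds as an endpoint-definition gap. One removal code is defined by provider, it overlaps with a code defined by reason, and neither document says which codes are events. If only 'Safety Reasons' is counted, the cumulative safety-related removal rate is biased downward by whatever share of safety removals is coded 'Unknown'.

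That share is not in the documents, and the effect is probably small. For perforation alone it is about 0.1 per 100 women if every expected case were so coded, and less if only some are. This rests on the protocol's background rate, the planned 1,750 LNG20 women and a crude proportion. Other safety removals done elsewhere would add to it by an unknown amount. The documents do not support reading the gap as the loss of all outside removals, or the exclusion of 'Non-Safety' removals as an error.

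**What to change.** - **Protocol 7.13:** code the action by the documented reason, whoever removed the IUS. Reserve 'Unknown' for removals whose reason cannot be obtained.
- **Existing data:** review removals already coded 'Unknown' and recode them from the adverse-event and removal records. Adverse events that end treatment must already be reported (Protocol 7.7), so no new data collection is needed.
- **SAP 11.9:** state which 7.13 codes are events for safety-related removal and how 'Unknown' is treated. Add a sensitivity analysis that counts the remaining 'Unknown' removals linked to an adverse event as safety-related.
- **Optional:** a table or cumulative rate of removal for any adverse event ('Safety' plus 'Non-Safety') would help readers interested in tolerability.

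The cost is a wording change, minor recoding and one sensitivity table. The reported rate may become slightly less favourable.
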